1 PROTOCOL SUMMARY

1.1 SYNOPSIS

Title: Randomized, Single-blinded, Controlled, Parallel-arm Study to Evaluate the Effect of Fast Bar™ on Physiological Fasting Condition

Study Description: This study evaluates how Fast Bar™, a specially formulated energy bar, affects the physiological condition in participants after an overnight fasting.

Participants will fast for 19 hours (Fast Group), consume a breakfast Bar (Breakfast Group) or a Fast Bar™ (Fast Bar Group) after an approximately 15-hour overnight fasting.

Participants will be assessed for physiological parameters associated with fasting.

Objectives:

Primary Objective:

The objective of this study is to evaluate the metabolic effects of consuming a novel food product (Fast Bar™), as compared to consuming a bar that resembles a typical breakfast, after an overnight fasting.

Secondary Objectives:

To assess the effect of a Fast Bar™ on facilitating fasting by modulating subjective variables.

Endpoints:

Primary Endpoint:

Physiological condition associated with fasting:

- Blood ketone (BHB) level
- Blood glucose level

Secondary Endpoint:

Questionnaires:

[figure not shown]
- Food diary
- Food evaluation
- Self-evaluation

Study Population: A total of 108, adult male and female, generally healthy subjects.

Phase: N/A

Description of Sites/Facilities Enrolling Participants:	Participants will be recruited via email or telephone. Participants will be consented via Zoom tele-conference. The study will be carried out at participants' home.
Description of Study Intervention:	Study subjects will consume a standardized ready-to-eat meal as dinner the day before testing and asked to fast for approximately 15 hours. Study subjects will either continue to fast for 6 hours (Fast Group), consume either a breakfast (Breakfast Group) or a Fast Bar™ (Fast Bar Group).
Study Duration:	3 months
Participant Duration:	2 days

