4 STUDY DESIGN

4.1 OVERALL DESIGN

This is quantitative research with a randomized, single-blinded, controlled, parallel-arm design.

Total length of subject participation is 2 days.

The study will be carried out off-site (at participants' home).

After the explanation of the study and informed consent signature, eligible participants will be randomized to three groups.

1. Subjects in all groups will be asked to consume a standardized ready-to-eat dinner meal before 5 pm on day 1.
2. Breakfast Group: overnight fasting (approximately 15 hours), then consume a breakfast on day 2;
3. Fast Bar Group: overnight fasting (approximately 15 hours), then consume a Fast Bar™ on day 2.
4. Water-only fasting group: overnight fasting (approximately 19 hours);
5. Subject all groups will be asked not to consume any food or calorie-containing drinks other than the study foods till 2 pm on day 2.

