5.3 LIFESTYLE CONSIDERATIONS

Participants will be asked to:

- Finish the dinner (provided) by 5 pm on day 1, followed by an approximate 15-hour water-only fast;
- Self-monitor blood glucose on day 1 (morning before breakfast) and on day 2;
- Self-monitor blood ketone (BHB) on day 1 (morning before breakfast) and on day 2.

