6 STUDY INTERVENTION

6.1 STUDY INTERVENTION(S) ADMINISTRATION

6.1.1 STUDY INTERVENTION DESCRIPTION

Participants will be asked to consume a ready-to-eat dinner before 5 pm on day 1.

Participants will be asked to refrain from consuming any food or drinks (except water) for 15 hours.

On day 2, subjects will be asked

- to continue the water-only fast for 4 more hours (Water Fast Group);
- to consume a breakfast, and then continue to water-only fast for 4 more hours (Breakfast Group);
- to consume a Fast Bar™, and then continue to water-only fast for 4 more hours (Fast Bar Group).

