6.1.2 DOSING AND ADMINISTRATION

Participants will undergo 15 to 19 hours of water-only overnight fasting.

Participants will consume a breakfast or a Fast Bar™.

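### Does the conflict over how long the day-2 fast lasts (4 or 6 more hours, or no food till 2 pm) affect the trial's results?

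*Combined protocol and SAP*

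**What the plan says.** Most of the text describes a fast that ends 4 hours after T0:

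- Synopsis, study description: "Participants will fast for 19 hours (Fast Group".
- Section 4.1, item 4: "Water-only fasting group: overnight fasting (approximately 19 hours".
- Section 6.1.1: the fasting arm is "to continue the water-only fast for 4 more hours (Water Fast Group". The Fast Bar arm eats its bar "and then continue to water-only fast for 4 more hours (Fast Bar Group", and the breakfast arm has the same 4 hours.
- Section 6.1.2: "Participants will undergo 15 to 19 hours of water-only overnight fasting".
- Schedule of Activities (1.3): the water-only row runs from T0 to T4, with example times of 8 am and 12 pm.

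Two statements point later:

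- Synopsis, description of the intervention: "Study subjects will either continue to fast for 6 hours (Fast Group". This line gives 6 hours for the Fast Group only.
- Section 4.1, item 5: subjects in all groups are "asked not to consume any food or calorie-containing drinks other than the study foods till 2 pm on day 2".

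Section 5.3 fixes the start of the fast: "Finish the dinner (provided) by 5 pm on day 1, followed by an approximate 15-hour water-only fast".

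**The concern.** The Synopsis and section 4.1 each seem to contain two different end times for the fast. The 6-hour line and the 2 pm line also fit each other, since 2 pm is exactly 6 hours after an 8 am T0. That makes it harder to dismiss either as an isolated misprint.

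If the two readings are true alternatives, someone who eats between T4 and 2 pm complies with section 6.1.1 and breaches section 4.1, item 5. That could matter for protocol deviations (10.1.10), for withdrawal because of non-compliance (7.2) and for the adherence review at the interim analysis (9.4.6). The reminder at the end of fasting (8.1) would have no single time. Participants carry out the fast at home, so a clear end time has practical value. Had any endpoint been measured after T4, the arms could also have been compared under different fasting conditions.

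**Working it through.** **Inputs.** Dinner finished by 5 pm and an overnight fast of about 15 h (5.3); T0 at 8 am and T4 at 12 pm as examples (1.3); 4 more hours (6.1.1); 6 hours (Synopsis); 2 pm (4.1, item 5).

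**Step 1: reproduce the plan's figure.** 5 pm + 15 h = 8 am (T0). 8 am + 4 h = 12 pm (T4). Total 15 + 4 = 19 h. This agrees with the Synopsis study description, 4.1 item 4 and the upper end of the range in 6.1.2.

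**Step 2: the 6-hour line.** 15 + 6 = 21 h, ending at 8 am + 6 h = 2 pm. The difference is 21 − 19 = 2 h, and 2/19 = 10.5%. The conflict on fast length is confirmed.

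**Step 3: can flexible clock times remove it?** The times in the Schedule are labelled as examples, so vary them and compute the gap from T4 to 2 pm:

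| Dinner ends | Overnight fast | T0 | T4 | Gap to 2 pm |
|---|---|---|---|---|
| 5 pm | 15 h | 8 am | 12 pm | 2 h |
| 4 pm | 15 h | 7 am | 11 am | 3 h |
| 5 pm | 16 h | 9 am | 1 pm | 1 h |
| 5 pm | 17 h | 10 am | 2 pm | 0 h |

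With a 5 pm dinner the gap closes only at an overnight fast of 17 h and a total of 21 h, which is not what the plan states. Scheduling does not explain the 2 pm time.

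**Step 4: is the 2 pm rule the same thing as the fast?** Section 6.1.1 bars all food and drink except water. Section 4.1, item 5 bars food and calorie-containing drinks, and does not call this a fast. A participant who takes only water until T4 and then no calories until 2 pm satisfies 6.1.1 and both items of 4.1. So item 5 does not contradict the 4-hour fast. The plan simply leaves the relation between the two unstated. The 6-hour line names only the Fast Group, so in the two bar arms there is no direct conflict on fast length.

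**Step 5: what is measured, and when?**

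| Item | Time after T0 | Within the 4 h common to all versions? |
|---|---|---|
| BHB at T3 (9.1, 9.4.2) | 3 h | Yes |
| BHB AUC (9.1, 9.4.2) | 0 to 4 h | Yes |
| Glucose and BHB fingersticks (1.3) | 0, 1, 2, 3, 4 h | Yes |
| Food evaluation (1.3) | 1 h | Yes |
| Self-evaluation (1.3) | 0 and 4 h | Yes |
| Food diary (1.3) | Day 1 | Yes, before T0 |

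Nothing is scheduled after T4. Section 4.4 ends the study on completion of the scheduled procedures.

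**Step 6: follow the downstream uses.** Withdrawal under 7.2 is discretionary and needs significant non-compliance; after T4 no scheduled procedure remains to be withdrawn from. Data from participants removed for non-compliance stay in the analysis (7.2, 9.3). The interim adherence review in 9.4.6 sets no threshold that depends on the hours after T4, and no scheduled instrument records intake in them.

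**The case for a change.** The best argument for acting is that the inconsistency sits in operative text, costs only a few words to remove, and leaves one behaviour open to two classifications. Section 10.1.10 counts any noncompliance as a deviation and sends deviations to the IRB, so food taken between T4 and 2 pm could be logged by one member of staff and ignored by another. The argument can be enlarged: if all 108 subjects kept the restriction for the extra 2 hours, that would be 108 × 2 = 216 participant-hours without a measurement.

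Part of this stands. The Synopsis does contradict itself, and nothing says whether the 2 pm rule is a margin after the fast or part of it. A count of deviations could differ slightly according to how it is read.

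The rest is weaker. It is too strong to say that the end of the fast and the meaning of a deviation are undefined: 6.1.1 and the Schedule give an end to the water-only fast, and 10.1.10 gives a general definition. The 216 hours assume one reading of item 5 and full retention, although section 9.2 allows for about 10% dropout or data loss, and the figure measures neither bias nor harm. No safety argument turns on the 2 hours either, since the plan's own rationale (2.1) describes fasts of 12 to 48 hours as considered safe, a range that contains both 19 and 21.

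**Conclusion.** The contradiction is genuine but editorial: 19 against 21 hours for the Fast Group, a difference of 2 hours falling wholly after the last scheduled measurement. Its effect on BHB at T3, on the 0 to 4 hour AUC and on the comparison of Fast Bar with breakfast is nil. The 2 pm food restriction is a separate point, compatible with a fast ending at T4, whose purpose is left unexplained.

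The two Synopsis lines, 4.1, 6.1.1 and 6.1.2 must be reconciled to one duration, with the relation of 2 pm to T4 and the arms it covers made clear. That choice belongs to the sponsor, and this review takes no view on it. Because the reconciliation alters no measurement, analysis or conclusion, no change to the statistical plan follows.

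This rests on two assumptions: participants keep the fast at least to T4, as every version requires, and expecting a later end to the restriction does not itself alter readings taken by T4. Participant-facing materials were not available, so nothing is claimed about them.

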1.2 SCHEMA

1.3 SCHEDULE OF ACTIVITIES (SOA)

	Screening	Day 1	Day 2				
Day		1	T0	T1	T2	T3	T4
Hours			Baseline	+1 h	+2 h	+3 h	+4 h
Example clock times			8 am	9 am	10 am	11 am	12 pm
Procedures							
Informed consent	X						
Randomization	X (1)						
Blood draw (Fingerstick)		X (morning, fasting)	X	X	X	X	X
• ketone (BHB)							
• glucose							
Intervention							
Healthy Eating Style	X (2)						
Dinner, followed by 15 h water-only fasting		X (before 5 pm)					
Breakfast Bar			X (after T0 test)				
Fast Bar™			X (after T0 test)				
Water-only fast			X	X	X	X	X
Questionnaires/ Surveys							
Demographics	X						
Contact Information	X						
Medical history							
Concomitant medications	X						
24-h dietary recall	X						
Food diary		X					
Self-evaluation			X (after T0 test)				X
Food evaluation				X			

(1) Subjects will be assigned to study arms according to the randomization scheme generated by using the web site Randomization.com (<http://www.randomization.com>).

(2) Subjects will be provided with a USDA MyPlate Plan according to his/her BMI and physical activity level (<https://www.choosemyplate.gov/resources/MyPlatePlan>) and encouraged to adopt the recommended healthy eating style for 2-3 days before starting the trial.

2 INTRODUCTION

2.1 STUDY RATIONALE

The objective of this study is to evaluate the metabolic effects of consuming a novel food product (Fast Bar™) after overnight fasting.

Interest in fasting-based programs (i.e. intermittent fasting) for improvement of health and longevity continues to grow [1-3]. While benefits of intermittent fasting have been convincingly demonstrated in rodent models, the more limited data in humans is less clear. As such, additional investigations of the

effects of fasting-based protocols in humans are needed. The short-term fasting (e.g. 12 to 48 hours in duration) utilized in many intermittent fasting programs are considered safe, but some individuals may find them subjectively difficult. As such, the question of whether the benefits of fasting can be obtained while small amounts of food are consumed is of substantial interest. An attractive strategy may be to consume small quantities of foods specifically formulated to maintain a fasted or pseudo-fasted state. If such a strategy is successful, the benefits of fasting may be maintained even though a small amount of food consumption, which will alleviate subjective feelings of hunger and promote adequate nutritional intake.

One commercially available product that is designed to be consumed during periods of intermittent fasting is the Fast Bar™ (www.fastbar.com), which stems out of the well-researched fasting-mimicking diet [4, 5] to assist prolonged fasting. The unique formulation of the Fast Bar™, which consists of nuts and other select ingredients, is thought to minimize deviations in metabolic biomarkers associated with a fasting state. This may allow for extension of a fasting period through reduced subjective difficulty of fasting. However, these items have yet to be evaluated for its effects during intermittent fasting through a controlled research trial. As such, the objective of this study is to evaluate the metabolic and subjective effects of consuming a novel food product (Fast Bar™) after a short period of fasting.

2.2 BACKGROUND

Negative energy balance induced by calorie restriction (CR) or increased energy expenditure induced by exercise (EX) improves all metabolic coronary heart disease (CHD) risk factors, including plasma LDL-cholesterol, total cholesterol/HDL ratio, HOMA-IR index, and CRP concentrations [6, 7]. However, chronic calorie restriction, whose beneficial effects have been known for decades, has not been adopted by even a small percentage of the US population, in part because compliance to chronic and extreme diets is very low.

In healthy human subjects, three monthly cycles of fasting-mimicking diet (FMD) lasting 5 days reduced body weight, trunk and total body fat, and blood pressure [5]. In the same study, a post hoc analysis demonstrated that body mass index, blood pressure, fasting glucose, triglycerides, total and low-density lipoprotein cholesterol, and C-reactive protein were more beneficially affected in those participants with the highest baseline levels for the same variables, suggesting that FMD may be particularly effective in participants with established metabolic syndrome. Moreover, FMD cycles restore insulin secretion and glucose homeostasis in both type 2 and type 1 diabetes mouse models. In mice, a 4-day fasting mimicking diet (FMD) induced a stepwise expression of Sox17 and Pdx-1, followed by Ngn3-driven generation of insulin-producing b cells, indicating that FMD promotes the reprogramming of pancreatic cells to restore insulin generation in islets from T1D patients and reverse both T1D and T2D phenotypes in rodent models [8].

The Fast Bar™ is designed to provide energy without interfering with the protective and metabolic effects of fasting. The Fast Bar™ diets consist of 100% ingredients, which are generally regarded as safe (GRAS).

2.3 RISK/BENEFIT ASSESSMENT

2.3.1 KNOWN POTENTIAL RISKS

A 14-18 hours overnight fasting is a common practice. However, it is possible that some participants may experience fatigue, weakness, low blood sugar.

Fingerstick is a common practice for checking blood glucose. Participants could experience pain, discomfort, bruising or infection (a slight risk any time the skin is broken). Fingerstick devices should never be used for more than one person.

Although participants will be screened for food allergies, it is possible that an allergic reaction could occur upon ingestion of the study foods.

2.3.2 KNOWN POTENTIAL BENEFITS

Short term known potential benefits:

N/A

Long term known potential benefits:

N/A

2.3.3 ASSESSMENT OF POTENTIAL RISKS AND BENEFITS

RISKS

The study intervention (overnight fasting and study food consumption) and procedure (fingerstick) pose a minimal risk to the study subjects.

BENEFITS

Participants may not receive any direct benefit from taking part in this study.

3 OBJECTIVES AND ENDPOINTS

The research questions to be addressed are:

1. What are the metabolic effects of consuming a Fast Bar™, as compared to consuming a typical breakfast, after an overnight fast?
2. Based on the observed metabolic effects, does consumption of a Fast Bar™ allow for maintenance of the fasting state?
3. Does consumption of a Fast Bar™ facilitate fasting by modulating subjective variables?

OBJECTIVES	ENDPOINTS	JUSTIFICATION FOR ENDPOINTS
Primary		
Physiological condition associated with fasting	
• Blood ketone (β-hydroxybutyrate, BHB) level• Blood glucose level	When hepatic glycogen stores are exhausted (after 12-24 hours of total fasting), the liver produces ketones (ketogenesis: acetoacetate (AA) and BHB) to provide an energy substrate for peripheral tissues.
Secondary		
Questionnaires	
• Food evaluation• Self-evaluation	The secondary objective is to assess the subjective variables

4 STUDY DESIGN

4.1 OVERALL DESIGN

This is quantitative research with a randomized, single-blinded, controlled, parallel-arm design.

Total length of subject participation is 2 days.

The study will be carried out off-site (at participants' home).

After the explanation of the study and informed consent signature, eligible participants will be randomized to three groups.

1. Subjects in all groups will be asked to consume a standardized ready-to-eat dinner meal before 5 pm on day 1.
2. Breakfast Group: overnight fasting (approximately 15 hours), then consume a breakfast on day 2;
3. Fast Bar Group: overnight fasting (approximately 15 hours), then consume a Fast Bar™ on day 2.
4. Water-only fasting group: overnight fasting (approximately 19 hours);
5. Subject all groups will be asked not to consume any food or calorie-containing drinks other than the study foods till 2 pm on day 2.

4.2 SCIENTIFIC RATIONALE FOR STUDY DESIGN

This research will allow for scientific evaluation of the application of the Fast Bar™ during intermittent fasting. That is, this research will allow for quantification of the changes in metabolic biomarkers after consumption of a Fast Bar™, following a period of acute fasting, to determine whether deviations from the fasted state are smaller and more transient than when consuming a breakfast bar. This comparison will facilitate a better understanding of whether the Fast Bar™ is a viable strategy for extending the benefits of intermittent fasting despite the consumption of food.

4.3 JUSTIFICATION FOR DOSE

Fasting leads to the mobilization of hepatic glycogen stores. When the glycogen stores are exhausted (after 12-24 hours of total fasting), the liver produces ketones (ketogenesis: acetoacetate (AA) and β -hydroxybutyrate (BHB) to provide an energy substrate for peripheral tissues. Consumption of food, depending on the composition of the food, i.e., the absolute levels and ratios of carbohydrate, protein and fat, may markedly affect the ketogenesis state. We hypothesis that the specially formulated Fast Bar™ will not significantly impact the overnight fasting-induced ketogenesis state.

4.4 END OF STUDY DEFINITION

The end of the study is defined as completion of the procedures shown in the Schedule of Activities (SoA) in the trial (Section 1.3).

5 STUDY POPULATION

5.1 INCLUSION CRITERIA

An individual of any race and ethnicity who meets all of the following criteria will be included for participation in this study:

- Ability and willingness to provide written informed consent;
- Ability and willingness to use Zoom teleconference;
- Ability and willingness to perform the study tests and adhere to study protocol (to the best of the participant's knowledge);
- 18-65 years of age (inclusive) at screening;
- BMI 20-35 kg/m² (inclusive) at screening;

- In good health (as determined by medical history to evaluate acute or ongoing chronic medical diagnoses/conditions that have been present for at least 90 days).

5.2 EXCLUSION CRITERIA

An individual of any race and ethnicity who meets any of the following criteria will be excluded from participation in this study:

- Has any medical disease or condition that, in the opinion of the principal investigator (PI) or appropriate study personnel, precludes study participation* (*Including acute, subacute, intermittent or chronic medical disease or condition that would place the subject at an unacceptable risk of injury, render the subject unable to meet the requirements of the protocol, or may interfere with the evaluation of responses or the subject's successful completion of this trial);
- History of gastric bypass (based on medical history provided at screening);
- Under medications aimed at keeping blood glucose under control (based on medical history provided at screening);
- Type 1 diabetes (based on medical history provided at screening);
- Taking insulin, insulin analogs, or octreotide (based on medical history provided at screening);
- Food allergies which would make the subject unable to consume the food provided (based on medical history and information provided at screening) (participants will be asked to review the ingredient lists for the dinner meal, the breakfast and the Fast Bar™, and to state that they are not allergic to the ingredients to the best of their knowledge);
- Women who are pregnant;
- Alcohol dependency (alcohol intake greater than two drinks per day for women and three drinks per day for men) (based on medical history and information provided at screening).

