6.2.2 FORMULATION, APPEARANCE, PACKAGING, AND LABELING

L-Nutra company handles the formulation, appearance, packaging and labeling of all the food products for this study.

The custom ready-to-eat dinner prior to fasting will be provided by Nutrition For Longevity, a subsidiary of L-Nutra.

Dinner meal ingredients: Sockeye Salmon, Organic Red Cabbage, Organic Cooked White Rice, Organic Stir Fry Greens, Organic Broccoli, Organic Cauliflower Rice, Organic Carrots, Organic Onion, N4L Imported EVOO, N4L Teriyaki Sauce (Organic Pineapple Juice, Organic Japanese Rice Wine, Organic Ginger Root, Organic Tamari), Organic Garlic, Organic Scallions.

Contains Fish, Soy, Tree Nuts.

The breakfast bar is formulated to mimic a typical breakfast in energy contents.

Breakfast ingredients: Tapioca Syrup, Dates, Almond Butter, Almonds, Soy Protein Crisps (Soy Protein Isolate, Rice Flour, Malt Extract (may contain wheat), Micellar Casein, Whey Protein Concentrate, Pea Protein, Flaxseed, Almond Protein, Maltodextrin, Sunflower Lecithin, Sea Salt, Natural Flavor. Contains Milk, Soy and Almonds. May contain Wheat.

Fast Bar™ ingredients: Macadamia Nuts, Pecan Pieces, Inulin, Almond Meal, Almond Butter, Honey, Coconut Flour, Flaxseed Meal, Vanilla Powder, Sea Salt, Rosemary oleoresin.

Product Contains: Tree nuts (almonds, coconut, macadamia nuts, pecans). Manufactured on equipment that also processes other tree nuts, peanuts, soy, wheat, egg, and milk.

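### The participant allergy statement in 5.2 covers only listed ingredients, while 6.2.2 declares peanut, egg and tree-nut allergens that the three ingredient lists do not show

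*Combined protocol and SAP*

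**What the plan says.** The food-allergy item in section 5.2 has two parts. The exclusion itself reads "Food allergies which would make the subject unable to consume the food provided (based on medical history and information provided at screening". A second part puts it into practice. Each person looks through what goes into all three foods, whatever arm they later join, and the declaration then required is worded "and to state that they are not allergic to the ingredients to the best of their knowledge".

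Section 6.2.2 gives the ingredients of each food and, next to them, allergen wording that goes further. For the Fast Bar there is a declaration, "Product Contains: Tree nuts (almonds, coconut, macadamia nuts, pecans". A separate sentence on shared equipment adds more: "Manufactured on equipment that also processes other tree nuts, peanuts, soy, wheat, egg, and milk". For the dinner the declaration is "Contains Fish, Soy, Tree Nuts".

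Section 2.3.1 names allergic reaction as a risk and refers to the screen: "Although participants will be screened for food allergies, it is possible that an allergic reaction could occur upon ingestion of the study foods". It does not mention shared equipment.

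**The concern.** The participant's statement is the only concrete allergy step that the protocol describes, and it is tied to ingredients. If an allergen is declared for a food but is missing from every ingredient list, a participant can follow 5.2 to the letter, answer truthfully, and still be given a food whose label warns of that allergen.

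What is at stake is participant safety. No effect on the BHB endpoints is claimed. Allergic reaction is one of the few risks that 2.3.1 names. The foods are eaten at home (4.1), and the sections on safety assessments (8.2) and safety oversight (10.1.6) are marked not applicable.

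**Working it through.** The plan gives no figure to reproduce. The check compares every allergen declared in 6.2.2 with the three ingredient lists that 5.2 puts before the participant.

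| Allergen | Where 6.2.2 declares it | Named source in any of the three ingredient lists |
|---|---|---|
| Fish | Dinner | Salmon (dinner) |
| Soy | Dinner, breakfast bar, Fast Bar equipment | Tamari (dinner), soy protein (breakfast bar) |
| Milk | Breakfast bar, Fast Bar equipment | Casein and whey (breakfast bar) |
| Wheat | Breakfast bar (possible), Fast Bar equipment | Note on malt extract inside the breakfast bar list |
| Almond, coconut, macadamia, pecan | Fast Bar; almond also in breakfast bar | Fast Bar list; almond also in breakfast bar list |
| Other tree nuts | Fast Bar equipment; dinner declares tree nuts without naming the kind | None |
| Peanut | Fast Bar equipment | None |
| Egg | Fast Bar equipment | None |

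**Fast Bar equipment.** The sentence names six allergen groups. Soy, wheat and milk are visible in another food's list, and because everyone reads all three lists, the statement reaches them. Peanut, egg and the other tree nuts are visible in none.

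**Dinner.** Three allergens are declared. Salmon accounts for fish and tamari for soy. No listed ingredient is named as a tree nut. The list may be incomplete, or the declaration may be precautionary or mistaken; the documents do not say which.

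**Who could pass the statement truthfully.** This could be a person allergic to peanut, a person allergic to egg, or a person allergic only to a tree nut other than almond, coconut, macadamia or pecan. A person allergic to tree nuts in general would meet them in the Fast Bar list and could not truthfully make the statement.

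**Who receives the foods.** Section 6.3 plans 12 blocks of 9, so 12 × 9 = 108 participants, allocated 1:1:1, so 108 / 3 = 36 to the Fast Bar. The shared-equipment wording concerns those 36. The dinner goes to every arm (4.1), so its tree-nut declaration concerns all 108.

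**Other parts of the screen.** Section 8.1 places medical history at screening and uses a health survey on medical history, conditions and medications. Neither description mentions food allergy. No section says whether shared-equipment contact counts as making a person unable to eat the food, so two screeners could read the exclusion differently.

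**The case against.** The strongest objection is that the participant's statement is not the whole screen. The exclusion rests on medical history and screening information as well, and the first exclusion in 5.2 gives wide discretion: "Has any medical disease or condition that, in the opinion of the principal investigator (PI) or appropriate study personnel, precludes study participation". A known peanut or egg allergy could come to light by either route. This stands. A reader might infer that 5.2 asks about ingredients and nothing else, so that an allergic participant is bound to be enrolled. The documents do not support that: passing is possible, not certain. These routes still do not close the gap, because no section says that they ask about the allergens in question.

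A second objection is that nothing shows the allergen wording is withheld. In 6.2.2 it is printed beside the ingredients, and the sheet that participants see may carry it too. The consent form, which might also carry it, is not in the text available. This stands as well. The gap is in what the protocol specifies and is not shown in practice.

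Third, the protocol has other safeguards. Participants are monitored by teleconference (6.4), adverse events are recorded (8.3.4), withdrawal for an adverse event is allowed (7.2), and 2.3.1 admits the residual risk. These are fair mitigations, but they act after the food is eaten or do not address the missing allergens.

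Finally, 5.2 and 6.2.2 do not contradict each other on peanut and egg, since 5.2 is merely silent on shared equipment. That is correct. The mismatch inside 6.2.2, between the dinner's list and its declaration, is a real inconsistency.

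**Conclusion.** The point holds as a gap in the specified allergy statement. Three declared allergen groups (peanut, egg, and tree nuts other than the four named) appear in no ingredient list, and one declared dinner allergen has no listed source. The first gap concerns the Fast Bar, planned for 36 participants, and the second the dinner, planned for 108. The conclusion assumes that participants are shown what 5.2 describes, namely ingredient lists, and that medical history is taken without a specific question on these allergens. If the screening form already does more, the protocol only needs to say so.

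Two stronger readings are tempting. A reader might put a probability on an allergic participant reaching the Fast Bar arm. That would need the prevalence of these allergies and the share that history or discretion would miss, and the documents give neither. Even then it would not be the chance of a reaction, because no contamination rate is given. A reader might also infer an imbalance in adverse events against the Fast Bar. Nothing in the documents supports that, and the dinner issue affects all arms alike.

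The matter should be put right because it bears on a named risk and the correction is small.

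**What to change.** Reconcile 5.2 with 6.2.2 so that the material participants review and respond to carries the full allergen wording of each of the three foods: ingredients, declared contents, possible contents and shared equipment. Resolve the dinner's tree-nut declaration against its ingredient list with the supplier before the lists are used, and correct whichever is wrong. How an allergy disclosed in this way bears on eligibility is for the sponsor and investigator to decide and is not proposed here.

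The cost is a wording change in 5.2 and on the screening form, plus one query to the supplier. The downside is small: possibly one or two more screen failures, which is a judgement, as the documents give no figure.
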